## **9.2 Withdrawal of Subjects from the Study**

All subjects are free to withdraw from participation at any time, for any reason, specified or unspecified, and without prejudice. This may include subjects who withdraw from study treatment early and who decline to continue to come in for remaining follow-up visits or it may include subjects who completed treatment and decline to come in for remaining follow up visits.

Reasonable attempts will be made by the investigator to provide a reason for subject withdrawals. The reason for the subject's withdrawal from the study will be specified in the subject's source documents. Subjects who withdraw from the study should be encouraged to come in for a final visit.

## **9.3 Replacement of Subjects**

Subjects who withdraw from the study will not be replaced.

## **10 DATA SAFETY MONITORING**

Monitoring for data integrity and safety will be the responsibility of the investigators, the FHCRC Institutional Review Board, and a study Data and Safety Monitoring Committee, which will be established prior to recruiting any participants. The following will be included in the monitoring plan for the DSMC: safety of participants and volunteers, reporting of adverse events, validity and integrity of the data, enrollment rate relative to expectation, retention of participants and adherence to protocol, and data completeness.

### **10.1 Adverse Event Reporting**

Adverse events for this study are expected to be very minimal since the diet and physical activity intervention activities have been safely used in many previous intervention studies without incident. Despite the low risk for adverse events, all study staff and investigators will carefully monitor and document any adverse events, which could include the following: bruising or fainting during the blood draws, injury from using the exercise equipment in the PHS Exercise Laboratory, injury from exercise at home (such as a fall) or a medical event during the treadmill test. All such adverse events will be reported to the Principal Investigator within 24 hours. Adverse event reporting to the IRO will occur within the required period of time depending on the nature and severity of the event.

### **10.2 Data Safety Monitoring Committee**

The initial meeting of the DSMC will have primary focus on a review of the proposed study protocol and determination of stopping rules. Due to the low-risk nature of the intervention study, we expect the DSMC to review study progress each year. Informal rather than formal interim analyses will be performed, since the primary endpoints will not be determined until the end of the study. For each DSMC meeting, statistical reports will be prepared four weeks in advance. Tabulations of the distributions of the important variables will be inspected to detect outlying values. After the file has been thoroughly checked, tables and graphs of the data will be made and compared with the previous report. This check will identify major changes in the data that might be indicative of computational or processing errors. Tables will include data presented by study arm. These reports will include adverse events and participant drop-outs. The report will be mailed to members of the DSMC two weeks prior to the meeting.

## **11 STATISTICAL METHODS AND CONSIDERATIONS**

**Primary Aim 1.** The primary analysis will compare change in fasting glucose level relative to baseline between the intervention and control arms. Global assessment of intervention effects will be evaluated using a two-sided t-test or Wilcoxon rank sum test if normality of the measurement is questionable (as determined by QQ-normal plots). Further analysis will quantify effects of patient age, BMI and other body composition measures on change in fasting glucose using linear regression. Differential effects between intervention and control arms will be quantified using interaction terms. All analyses will compare effects based on intention-to-treat.

**Primary Aim 2.** Additional analyses will compare changes in levels of C-peptide, insulin, IGF-1, IGF-BP3, and adiponectin relative to baseline measurements between the intervention and control arms. As in Aim 1, we will compare global and subgroup effects based on intention-to-treat analyses.

**Primary Aim 3.** We will test whether the change in expression of IR, IGF-1R, and AKT on prostate cancer epithelial cells from follow-up surveillance biopsy (6 months post-randomization) relative to 'baseline' (biopsy ~6 months prior to randomization, see Fig. 3) differs between intervention and control arms. Global assessment of intervention effects will be evaluated using a two-sided t-test (or Wilcoxon rank sum test). Linear regression will be used to assess associations of IR, IGF-1R, and AKT expression with systemic measures of glycemic control at 6 months. Exploratory analyses will also evaluate associations between adverse pathology, biomarkers of glycemic control and IR/IGF-1R/AKT expression.

**Primary Aim 4.** We will test whether PCa patients randomized to the intervention arm are able to sustain the beneficial changes in weight and glucose regulation an additional 6 months after the active intervention. We will follow the DPP research group characterization of sustained weight loss as maintenance of a 7% reduction in weight and sustained glucose regulation as maintenance within 5% of 6-month levels. Because not all participants will achieve 7% weight loss at 6 months, we will look in the subset of participants who did and did not achieve this goal both separately and combined. A one-sample test of proportions will be used to determine whether the proportion of participants that are able to sustain lifestyle changes differs from zero.

**Secondary Aim 1.** We will test whether the change in HRQOL, namely urinary and sexual QOL and bother, relative to baseline, differs between the intervention and control arms. Intervention effects will be evaluated using a two-sided t-test, and models will be adjusted for age, SES, marital status, and baseline BMI. The minimally important difference for the HRQOL instruments will be a mean difference of at least 5 points.

**Secondary Aim 2.** We will use a two-sample test of proportions to determine whether the proportion of participants with adverse pathology (Gleason upgrading, increase in number of positive cores, cores>50% positive) on follow-up surveillance biopsy differs between intervention and control arms.

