STATISTICS Primary Analysis Plan	
Aims 1 and 2: Global assessment of intervention effects will be evaluated using a two-sided t-test or Wilcoxon rank sum test if normality of the measurement is questionable (as determined by QQ-normal plots). Further analysis will quantify effects of patient age, BMI and other body composition measures on change in fasting glucose using linear regression. Differential effects between intervention and control arms will be quantified using interaction terms. All analyses will compare effects based on intention-to-treat.
 
Aim 3: Global assessment of intervention effects will be evaluated using a two-sided t-test (or Wilcoxon rank sum test). Linear regression will be used to assess associations of IR, IGF-1R, and AKT expression with systemic measures of glycemic control at 6 months.
 
Aim 4: We will follow the DPP research group characterization of sustained weight loss as maintenance of a 7% reduction in weight and sustained glucose regulation as maintenance within 5% of 6-month levels. Because not all participants will achieve 7% weight loss at 6 months, we will look in the subset of participants who did and did not achieve this goal both separately and combined. A one-sample test of proportions will be used to determine whether the proportion of participants that are able to sustain lifestyle changes differs from zero.

Rationale for Number of Subjects	Our power calculations give the minimally detectable intervention effects for endpoints in Primary Specific Aims, setting two-sided alpha error at 5% and power at 80%. We have set a sample size of 100 in each of the intervention and control arms, based both on our overall evaluation of minimum detectable differences across the range of study endpoints and on a reasonable estimate of the number of men we can recruit. The sample size allows for a drop-out rate of 5%, and power calculations assume correlations of 0.70 between baseline and follow-up measures.

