## 7.3 Randomization

Participants will be randomly assigned to either the intervention or control arm using a computerized program. In order to evenly distribute men to treatment arm, randomization will be blocked on BMI (25-29.9 or 30+) and age (<65years or 65+).

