## 7.5 Clinical Assessments

Study visits will occur at baseline, 3, 6 and 12 months. During study visits, participants will undergo anthropometrics, fasting blood studies and/or complete physical activity, food diaries and HRQOL questionnaires. Assessments at 6 months will be used to evaluate the effectiveness of the intervention, and at 12 months will evaluate maintenance of the intervention.

Anthropometric Measurements. Height will be measured at baseline only, and weight, waist (1" above umbilicus), hip circumferences will be measured at baseline, 3, 6 and 12 months. Dual x-ray absorptiometry (DXA) using a GE Lunar iDXA will be obtained to measure overall percent body fat, lean mass and total bone density at baseline and 12 months.

Twelve-hour fasting blood. Fasting blood samples will be collected at baseline, and at 3, 6, and 12 months. Vacutainers will be labeled with participants' study ID and date, processed within 1 hour of collection and stored at -70°C.

Prostate Tissue. As part of the consent to participate in this study, participants are asked to give permission to investigators to allow a) the collection of two extra prostate biopsy cores during their standard-of-care biopsy (UW and VA participants only), and b) access to pathology tissue from a pre-study biopsy (that was already collected as part of routine medical care for diagnostic purposes) to be used for this study (UW and VA participants only). For VA patients, separate consent allowing the collection of extra biopsy cores during a standard-of-care biopsy, and allowing access to biopsy tissue after used for diagnostic purposes will be obtained at the VAPSHCS by VA study staff on the day of their scheduled biopsy. For participants who are not patients at UW or the VA, since the collection of extra biopsy cores is not possible, they will be asked to sign a separate "Release of Information" allowing access to prostate biopsy tissue collected as part of their routine care. Tissue blocks, fixed in formalin and embedded in paraffin (standard for AS biopsies), will be sent to [name] laboratory. Participants will be enrolled on study so that the intervention calendar coincides with routine clinical care; no extra biopsies will take place outside of the routine clinical care. Tissue blocks will be cut and sections mounted on charged slides.

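### Free improvement: the serum treatment tests and the quality-of-life models leave out the outcome's own baseline value; against the planned t-test on change, adjusting for it cuts variance by 15% at the stated correlation of 0.70

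*Combined protocol and SAP*

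**What the plan says.** Section 11 defines the Aim 1 outcome as change in fasting glucose and gives the treatment test as follows: "Global assessment of intervention effects will be evaluated using a two-sided t-test or Wilcoxon rank sum test if normality of the measurement is questionable". Aim 2 follows Aim 1: "Additional analyses will compare changes in levels of C-peptide, insulin, IGF-1, IGF-BP3, and adiponectin relative to baseline measurements". Aim 3 uses the same pair of tests on change in tissue expression. The synopsis agrees: "Global assessment of intervention effects will be evaluated using a two-sided t-test or Wilcoxon rank sum test".

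Regression comes in only afterwards: "Further analysis will quantify effects of patient age, BMI and other body composition measures on change in fasting glucose using linear regression". Baseline glucose is not among the listed terms, and this regression is not the treatment test. Section 7.3 uses BMI and age groups in the randomization; neither enters the Aim 1-3 treatment tests. The Secondary Aim 1 models adjust for age, SES, marital status and baseline BMI, but not for the baseline score of the scale being analysed.

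The baseline data will exist. Section 7.5 states: "Fasting blood samples will be collected at baseline, and at 3, 6, and 12 months". The quality-of-life questionnaires are also scheduled at baseline. The time point for efficacy is clear: "Assessments at 6 months will be used to evaluate the effectiveness of the intervention". Section 11.1 assumes a correlation of 0.70 between baseline and follow-up, 100 men per arm and 5% drop-out.

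**The concern.** A comparison of change scores subtracts the whole baseline value, which fixes its slope at 1. If baseline and follow-up correlate at 0.70 with equal SDs, the slope that minimises the variance is 0.70, so the change score over-corrects and adds noise. A model with baseline as a covariate estimates the slope from the data.

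At stake is precision that needs no extra men and no extra measurements. Section 11.1 says the sample size was set partly by how many men can be recruited, and section 9.3 does not replace withdrawals, so precision is hard to buy in other ways.

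**Working it through.** **Inputs.** r = 0.70, two-sided 5%, 80% power, 100 per arm less 5% = 95 per arm (section 11.1). SDs: glucose 12.6 mg/dL (Table 4); EPIC-Urinary bother 14 and EPIC-Sexual bother 23, with a 5-point difference of interest (Table 5 and section 11). The documents give no follow-up SD, so k = follow-up SD / baseline SD is assumed to lie between 0.8 and 1.2.

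**The plan's own figures.** Table 4 prints a minimum detectable difference (MDD) of 5.6 mg/dL for glucose. A change score at r = 0.70 and 95 per arm gives 3.99, not 5.6. A change score at r = 0.40 gives 5.64 (5.61 by the normal approximation). The Table 5 powers of 69% and 32% for the two EPIC scales reproduce with the unreduced SD at 95 per arm. So neither figure uses 0.70. That mismatch is a separate matter, but it is why the starting values below differ from the printed ones.

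**Variance of the treatment comparison**, in units of baseline SD²:

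- change score: 1 + k² − 2rk
- baseline-adjusted: k²(1 − r²)

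At k = 1 these are 0.60 and 0.51; the ratio is 0.85, a 15% cut. On 190 evaluable men that is worth 190 × (1/0.85 − 1) = 33.5 more men.

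| k | Change | Adjusted | Cut |
|---|---|---|---|
| 0.8 | 0.520 | 0.326 | 37.2% |
| 0.9 | 0.550 | 0.413 | 24.9% |
| 1.0 | 0.600 | 0.510 | 15.0% |
| 1.1 | 0.670 | 0.617 | 7.9% |
| 1.2 | 0.760 | 0.734 | 3.4% |

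The cut is zero at k = 1/r = 1.43 and is not negative at any k in large samples. Simulation at k = 0.8, 1.0 and 1.2 gave 36.7%, 15.1% and 2.8%. At r = 0.40 and k = 1 the cut would be 30%.

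**Glucose.** At k = 1 the SD falls from 12.6 × √0.60 = 9.76 to 12.6 × √0.51 = 9.00. The normal approximation, 2.802 × SD × √(2/95), gives 3.97 and 3.66. The noncentral t (188 and 185 degrees of freedom) gives 3.99 and 3.68 mg/dL. Power at 5.6 mg/dL goes from 97.6% to 98.9%.

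**EPIC, 5 points, change score to baseline-adjusted.**

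| Scale | k = 1.0 | k = 1.2 | k = 0.8 |
|---|---|---|---|
| Urinary bother | 88.5 to 92.9% | 80 to 82% | 92 to 99% |
| Sexual bother | 49 to 55% | 40 to 41% | 54 to 74% |

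These take the four listed covariates to explain nothing. If they explain 20% of the variance in both models (assumed), the k = 1 figures are 94.2 to 96.9% and 58 to 65%.

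**Skewed markers.** SD/mean in Table 4 is 0.12 for glucose (12.6/106.3), 0.32 for IGF-1 and 0.23 for IGF-BP3, but 0.71 for C-peptide (1.2/1.7), 0.74 for insulin, 0.64 for adiponectin and 1.13 for the insulin receptor (34/30). The second group suggests skew, so the plan's rule may well send those markers to Wilcoxon. Simulated power follows, with assumed lognormal data at the Table 4 means and SDs, r = 0.70 and 95 per arm:

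| Marker and assumed effect | t on change | Wilcoxon on change | Raw-scale adjusted | Log-scale adjusted |
|---|---|---|---|---|
| C-peptide, 14% proportional | 44% | 51% | 54% | 66% |
| C-peptide, same-size additive shift | 43% | 66% | 50% | not used here |
| Insulin receptor, 30% proportional | 72% | 91% | 88% | 99% |

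The log-scale gain combines the transformation and the covariate, and is shown for proportional effects only.

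**The case against.** The strongest objection concerns the comparator. The plan is a t-test or, where normality is doubtful, a Wilcoxon test, and the 15% is measured against the t-test alone. This stands. In the simulation a raw-scale adjusted model beats Wilcoxon by only 3 points for C-peptide under a proportional effect, loses 16 points under an additive shift, and loses 3 points for the insulin receptor. Replacing Wilcoxon by a raw-scale linear model for skewed markers could therefore cost power.

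The second objection concerns tissue. The Aim 3 baseline is a biopsy taken about six months before randomization, and the score is a semi-quantitative composite with a floor at zero. The extra cores are limited: "the collection of two extra prostate biopsy cores during their standard-of-care biopsy (UW and VA participants only". Other men are asked to release routine tissue, and the number of pairs is not given. This also stands: no tissue gain is shown.

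Third, the gain is small where it matters most. Glucose power at 5.6 mg/dL is already above 97% at r = 0.70, EPIC-Sexual bother stays below 80%, and at k = 1.2 little is left. That is fair, and it limits the point to an inexpensive improvement. The mismatch between 0.70 and the tables does not reverse the direction: at k = 1 a lower correlation makes the gain larger.

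**Conclusion.** The point holds as one of efficiency. For glucose, IGF-1 and IGF-BP3, and for the Secondary Aim 1 scales, adding the baseline value cuts variance by 15% relative to the t-test on change, at r = 0.70 with equal SDs. The range is 3% to 37% for an SD ratio of 1.2 to 0.8. This assumes roughly symmetric data, 95 evaluable men per arm and the stated correlation, which the printed tables do not use.

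A reader might infer two stronger things. One is that the planned tests are wrong because they omit baseline and the randomization factors. They are not: in a randomized comparison the unadjusted tests are valid, and no gain is claimed here from the BMI and age strata. The other is that the 15% applies across Aims 1 to 3. The documents do not support that: the Wilcoxon branch is part of the plan, several Table 4 SDs suggest skew, and for tissue neither the usable correlation nor the number of pairs is known.

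**What to change.** In section 11 and the synopsis, fixed before outcome data are seen:

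- **Glucose, IGF-1, IGF-BP3:** make the primary test a linear model of the 6-month value on arm, baseline value, BMI stratum and age stratum. Report the adjusted mean difference, and keep the t-test or Wilcoxon on change as sensitivity analyses.
- **C-peptide, insulin, adiponectin:** prespecify the same model with outcome and baseline on the log scale, reported as a ratio of geometric means. Do not replace Wilcoxon with a raw-scale model.
- **Secondary Aim 1:** add the baseline score of the same scale to the listed covariates.
- **Aim 3:** leave the test as planned, or add a baseline-adjusted analysis as a sensitivity analysis only.

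The cost is SAP wording and one regression per endpoint; no new data are needed. The serum model uses three more degrees of freedom (188 to 185), and chance covariate imbalance can take back up to about 1 point of power. For the log-scale markers the effect becomes a ratio, so it is no longer in Table 4 units.

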#### **1.4 Diabetes Prevention Program**

The DPP studied over 3,000 participants with elevated fasting glucose levels randomized to metformin, a 6-month lifestyle modification program or placebo. The goal of the lifestyle modification program was a 7% reduction in body weight through a structured dietary program and at least 150 minutes of weekly physical activity. The lifestyle intervention decreased incident diabetes mellitus (DM) by 58% vs. controls, while metformin reduced incident DM by 31%. Fasting glucose declined from a mean of 107 to 101 mg/dl in the lifestyle group whereas no change was seen in the placebo group. Long term follow-up of the DPP has demonstrated sustained weight loss at 10 years, which is an important consideration as other studies of dietary interventions in men with PCa have used diets that are difficult to maintain over the long-term (e.g., vegan, low glycemic and prepared meals). The results of the lifestyle intervention have also been found to be cost-effective and cost saving. A meta-analysis of weight loss studies based on the DPP lifestyle modification program consistently shows statistically significant and clinically relevant reductions in weight; however, the majority of participants in those studies were women and no studies to date have been conducted in older men with cancer. Despite this, there are indications that older men may be an ideal population for the DPP lifestyle intervention. Older participants ( $\geq 60$  years) compared to younger groups (25-44 yrs. and 45-59 yrs.), had the greatest weight loss (mean -6.4 kg vs. -4.1 and -5.0 kg respectively,  $p < 0.001$ ) and more commonly met the exercise goal (48% vs. 34% and 38% respectively,  $p < 0.001$ ). The lifestyle intervention was more effective than metformin at weight loss with increasing age ( $p = 0.005$ ). In addition, compared to women, men lost more weight ( $p < 0.01$ ) and performed higher levels of physical activity ( $p < 0.05$ ) in the lifestyle intervention. However, since only 20% of participants were older than 60 years of age, fewer than 1/3 of participants were men, and none of the participants had cancer, whether these results will have similar effects in a PCa population are unknown, but certainly these data provide evidence that the DPP intervention can succeed in this population. Thus, the DPP intervention offers a novel strategy to improve PCa patient outcomes and yield insights on biological pathways by which obesity may delay or prevent disease progression.

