## 5 CRITERIA FOR EVALUATION

### 5.1 Primary Endpoint

The primary endpoints for each of the primary aims are:

**Primary Aim 1:** change in fasting glucose levels relative to baseline between the intervention and control arms.

**Primary Aim 2:** change in fasting C-peptide, insulin, IGF-1, IGF-BP3, and adiponectin levels relative to baseline between the intervention and control arms.

**Primary Aim 3:** change in expression of IR, IGF-1R, and AKT on prostate cancer epithelial cells from follow-up surveillance biopsy (6 months post-randomization) relative to 'baseline' (biopsy ~6 months prior to randomization).

**Primary Aim 4:** will test whether PCa patients randomized to the intervention arm are able to sustain the beneficial changes in weight and glucose regulation an additional 6 months after the active intervention.

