### 11.1 Sample Size and Randomization

Our power calculations give the minimally detectable intervention effects for endpoints in Primary Specific Aims, setting two-sided alpha error at 5% and power at 80%. We have set a sample size of 100 in each of the intervention and control arms, based both on our overall evaluation of minimum detectable differences across the range of study endpoints and on a reasonable estimate of the number of men we can recruit. The sample size allows for a drop-out rate of 5%, and power calculations assume correlations of 0.70 between baseline and follow-up measures.

Table 4 gives the minimally detectable differences between treatment arms for serum and tissue biomarkers of glucose regulation. We have used a variety of data sources to complete these tables, attempting whenever possible to use data generated from human studies. For serum biomarkers of glucose regulation, we use data from our own pilot study and the PCPT, and for tissue expression of IR/IGF-R1 and AKT we use data from Cox et al. The minimum detectable intervention effects range from 5.3% for serum glucose to 33.1% for insulin. Previous studies have shown that dietary change can induce the following intervention effects: 7% for fasting glucose, 40% for insulin and 2.2 % for adiponectin. Our pilot study based on the DPP demonstrated an intervention effect of ↑9.7% for IGFBP3, ↓38% for insulin and ↓14% for C-peptide. Based on these observations, we will have good power to detect changes in all serum biomarkers of glucose regulation, consistent with those seen in other human intervention studies.

For expression of IR, IGF-1R and AKT on surveillance prostate biopsies, the minimum detectable intervention effects are 29.2%, 46.3% and 26.5%, respectively. Previous experimental studies in animals have

**Table 4. Minimal detectable differences in serum and tissue biomarkers at 80% power,  $\alpha=0.05$  given a sample size of 200 (100 in each of the lifestyle intervention and control arms)**

Biomarker	Baseline Mean (SD) or n (%)	Minimum Detectable Difference (MDD)	
		Mean	% of mean
Primary Aim 1 - Serum			
Fasting glucose, mg/dL	106.3 (12.6)	5.6	5.3%
Primary Aim 2 - Serum			
C-peptide, ng/mL	1.7 (1.2)	0.54	31.6%
Insulin, pmol/L	138.0 (102.0)	45.7	33.1%
IGF-1, ng/mL	232.7 (75.4)	33.8	14.5%
IGF-BP3, ng/mL	4317.6 (975.2)	436.5	10.1%
Adiponectin, ug/mL	6.1(3.9)	1.8	29.0%
Primary Aim 3 – Tissue			

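### Aim 4's sustained-glucose rule has no baseline condition and no direction, so it cannot separate maintenance from no effect and separates maintenance from relapse only weakly

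*Combined protocol and SAP*

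**What the plan says.** Section 5.1 sets the purpose of Primary Aim 4: to test whether men in the intervention arm "sustain the beneficial changes in weight and glucose regulation an additional 6 months after the active intervention".

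Section 11 (Primary Aim 4), and the synopsis in the same words, turn the glucose part into a yes/no classification of each man: "sustained glucose regulation as maintenance within 5% of 6-month levels". Nothing more is said about glucose. The weight criterion in the same sentence is a 7% reduction, so it does have a direction.

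The only subsetting is by whether the 7% weight goal was met at 6 months: "we will look in the subset of participants who did and did not achieve this goal both separately and combined". The test is a one-sample test of "whether the proportion of participants that are able to sustain lifestyle changes differs from zero".

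Section 11.1 gives no expected proportion, power or precision for Aim 4. For the biomarkers generally it says that "power calculations assume correlations of 0.70 between baseline and follow-up measures".

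**The concern.** A benefit can be sustained only if there was one, and it is sustained if the later value is as good or better. The rule encodes neither condition. Two cases show the effect of the wording:

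- 106, then 110, then 110 mg/dL at baseline, 6 and 12 months: worse than baseline throughout, yet classed as sustained (0% change from month 6).
- 106, then 100, then 94 mg/dL: improving throughout, yet classed as not sustained (a 6% fall from month 6).

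The weight-based subsets do not screen out the first case, because they do not depend on glucose and are also pooled.

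At stake is the glucose half of a declared primary aim. A proportion that is about the same for an intervention that never worked as for one whose benefit was kept cannot support a statement about maintenance. The fault lies in how each man is classified. It is separate from the choice of zero as the null value, and changing that value would leave the classification as it is.

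**Working it through.** **Inputs**

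- Fasting glucose 106.3 (SD 12.6) mg/dL: Table 4, Section 11.1.
- Correlation r = 0.70: Section 11.1, stated for baseline and follow-up. Using it for the 6- and 12-month pair is an assumption, so a range is shown.
- Fall by month 6 of 6 mg/dL: Section 1.4, "Fasting glucose declined from a mean of 107 to 101 mg/dl in the lifestyle group". Section 11.1 also cites "7% for fasting glucose" from earlier dietary studies.
- 95 men: 100 per arm less 5% drop-out.

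**The plan's own figure.** None exists for Aim 4. The nearest is the Table 4 minimum detectable difference for glucose, 5.6 mg/dL. With the stated inputs, (1.96 + 0.84) × 9.76 × √(2/95) = 3.97 mg/dL, so 5.6 is not reproduced. It is reproduced with r = 0.40 at 95 per arm (5.61), or with r = 0.70 at about 47 per arm. Since 0.40 may be the value actually used, the range below starts there.

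**Step 1: the average man, without random variation.** Full relapse from 101 to 107 is 6/101 = +5.9% of the 6-month level. Reversing a 7% fall is 1/0.93 − 1 = +7.5%. Both lie just outside the 5% band. Full relapse would pass only if the original fall was at most 1 − 1/1.05 = 4.76% of baseline.

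**Step 2: with the plan's variability.** SD of change = 12.6 × √(2 × (1 − 0.70)) = 9.76 mg/dL. The band after a 6 mg/dL fall is 5% of 100.3 = 5.0 mg/dL.

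- Held: P(|N(0, 9.76)| < 5.0) = 39%.
- Fully relapsed: P(|N(6, 9.76)| < 5.0) = 33%.
- Never improved: band 5% of 106.3 = 5.3 mg/dL; P(|N(0, 9.76)| < 5.3) = 41%.

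A three-visit normal simulation with equal correlations, in which the band follows each man's own 6-month value, gives the following percentages classed as sustained:

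| r | Held | Fully relapsed | Never improved |
|---|---|---|---|
| 0.4 | 28 | 27 | 30 |
| 0.7 | 39 | 34 | 41 |
| 0.8 | 47 | 37 | 50 |
| 0.9 | 62 | 41 | 65 |

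If glucose falls a further 6 mg/dL by month 12, the figure at r = 0.70 is 32%, no better than full relapse.

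Never improved scores at or above held at every r shown, for a structural reason: the rule sees only the change from month 6 to month 12, and that averages zero in both cases. The small excess arises because 5% of a higher level is a wider band.

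**Step 3: who is misclassified at r = 0.70 with the benefit held.** About 30% of men fail only because their glucose fell by more than 5%. About 25% of those classed as sustained had no improvement at month 6.

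**Step 4: one-sided reading** (no more than 5% above the 6-month level), r = 0.70: held 69%, relapsed 46%, never improved 70%.

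**Step 5: precision.** For a proportion of 39% in 95 men the 95% CI half-width is 1.96 × √(0.39 × 0.61/95) = 9.8 points, wider than the 5-point gap between held and relapsed. For a mean change it is 1.96 × 9.76/√95 = 2.0 mg/dL, against a difference of 6 mg/dL between those two states.

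**The case against.** A reader might infer that the rule cannot tell maintenance from full relapse at all. The documents do not support that. At their own mean effects an average full relapse lands outside the band (Step 1), and separation improves as the correlation rises, to 62% against 41% at r = 0.9. Weak separation at the plan's stated correlation is as far as the numbers go.

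The two-sided reading may not be what the authors meant. Since the aim is about keeping a benefit, no more than 5% worse is a plausible intention. It widens the gap between held and relapsed to 23 points (69% against 46%) and removes the penalty for further improvement. This stands as a reason to state the direction. It does not repair the missing baseline condition, because held and never improved still coincide.

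A reader might also infer that measurement noise decides most classifications. The SD of 9.76 mg/dL mixes assay and day-to-day variation with real differences in how men change. The documents give no within-man reliability for glucose, and they do specify fasting samples and duplicate assays. That stronger claim is not made here.

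Finally, Aim 1 tests the glucose change against control, and Section 4.1 says that baseline, 6- and 12-month glucose measures will be compared. This helps at group level, since a null Aim 1 result would warn the reader. But Section 4.1 gives no method, Section 11 does not attach that comparison to Aim 4, and the Aim 4 classification would still be reported as written. Section 11 credits a DPP characterisation. Whether that source carries an improvement condition for glucose cannot be checked from these documents.

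**Conclusion.** The concern holds in this form. The glucose rule for Primary Aim 4 lacks a baseline condition and a direction. Its failure to separate maintenance from no effect follows from its structure: it appears at every correlation tried from 0.4 to 0.9, and on the one-sided reading at r = 0.70. Its separation of maintenance from relapse is weak on the literal reading at r = 0.70 (39% against 34%) and depends on the correlation and the direction assumed.

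These sizes rest on normal distributions, an SD of 12.6 mg/dL at each visit, a 6 mg/dL fall, and the stated correlation carried over to the 6- to 12-month pair. The weight half of Aim 4 and Aims 1 to 3 are not affected.

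**What to change.** In Section 11 and the synopsis, make the main glucose result for Aim 4 two estimates reported together, each with a 95% CI: the mean change in fasting glucose from 6 to 12 months, and from baseline to 12 months. As a pair they separate the scenarios (expected values in mg/dL):

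| True state | 6 to 12 months | Baseline to 12 months |
|---|---|---|
| Held | 0 | −6 |
| Fully relapsed | +6 | 0 |
| Never improved | 0 | 0 |
| Further improved | −6 | −12 |

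If a responder proportion is kept, label it descriptive, state its direction (12-month value no more than 5% above the 6-month value), and require improvement from baseline at month 6. Add a note that selecting men who improved at month 6 selects partly on noise: among them, at r = 0.70, about 62% meet the criterion if the benefit is held, 36% if it is lost, and 56% if there never was one. It should therefore not carry the conclusion.

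The cost is wording. Fasting blood is already drawn at baseline, 6 and 12 months (Section 7.5). The responder denominator shrinks: with about 27% of men not improved at month 6 under a 6 mg/dL mean fall, roughly 0.73 × 95 = 69 men remain.
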